2.3. Study Design

Overview of Study Design and Key Features	
Note: Protocol Amendment #3 extends allowable duration from <24h to <48h (start of mechanical ventilation)	
 
Start of mechanical ventilation via endotracheal tube
 
 • Echocardiograms (24h apart) • Lung function measurements and ventilator settings • Blood draw for RAS peptide and biomarkers (+/-30min of echocardiograms) 	
Design Features	
 • "Low-interventional" study • No investigational product will be administered • A maximum of 150 participants are anticipated to be enrolled • Participants enrolled following intubation and mechanical ventilation • Participants evaluated over a 3-day period using standard-of-care investigations, including TTE and/or TOE echocardiography • Additional investigations limited to blood samples for RAS peptides and other disease biomarkers • Purpose is to investigate the association of RAS peptides with indicators of right ventricular (RV) function in participants requiring acute mechanical ventilation
Dosing	
 • Not applicable
Treatment Assignment	
 • Not applicable
Interim Analysis	
 • Due to the early termination of the study no interim analysis will take place.

2.4. Statistical Hypotheses / Statistical Analyses

This study is designed to test the hypothesis that an association exists between RAS peptides, primarily plasma Ang II and Ang(1-7) levels, and RV function in mechanically ventilated patients. No formal statistical hypotheses are being tested in this exploratory study.

3. PLANNED ANALYSES

3.1. Interim Analyses

Table 1 Interim analyses

None of the planned interim analyses will take place in study 205821 due to the decision to terminate the study early.

The original interim analysis strategy was going to examine data at

- IA1: Approximately 25 evaluable subjects (Note: This was scheduled for Jan 2019 but delayed due to technical issues with the assay for RAS peptides and the study was terminated before the RAS data became available)
- IA2: Approximately 50 evaluable subjects.
- IA3 (Optional): Approximately 100 evaluable subjects

3.2. Final Analyses

The final planned analyses will be performed after the completion of the following sequential steps:

1. All subjects have completed the study as defined in the protocol (i.e. after the last participant has completed their 28-day follow-up).
2. All required database cleaning activities have been completed and final database release and database freeze has been declared by Data Management.
3. Protocol deviation reviews have taken place (See Section 4.1)

(Note: as there is no randomisation and no treatment intervention, the usual steps pertaining to unblinding and release of randomisation codes do not apply.)

4. ANALYSIS POPULATIONS

Population ¹	Definition / Criteria	Analyses Evaluated
Screened	All participants who have been screened.	
• To aid construction of Consort diagram in any publication
Enrolled	All participants who had passed screening and who had appropriate informed consent (via any of the processes described in the protocol).	
• Summary of Subject Status and Reason for Study Withdrawal• Summary of Study Populations• Summary of Exclusions from the

Population ¹	Definition / Criteria	Analyses Evaluated
		Safety/Completed/ Evaluable Populations
Safety	All participants for whom at least one echocardiograph and/or blood sample has been taken, and who did not retrospectively withdraw the consent.	
 • Study population (excl. specific tables mentioned below) • Safety
Evaluable	All participants for whom PASP, RV size ratio, Ang II and Ang(1-7) data have been recorded for at least one study time point, and who did not retrospectively withdraw the consent (and who still had at least one study time point of data remaining after accounting for any prohibited concomitant medications (for example but not limited to renin inhibitors, ARBs or ACE inhibitors) – See Section 10.1.1).	
 • Pharmacodynamic/ Biomarker (excl. disease diagnosis status)
Evaluable with Prohibited Con Meds	All participants in the Evaluable population plus any participants who were excluded from the Evaluable population because of prohibited concomitant medications (for example but not limited to renin inhibitors, ARBs or ACE inhibitors)	
 • Sensitivity for Primary analysis (conditional on number of prohibited con meds)
Completed ²	All participants for whom PASP, RV size ratio, Ang II, and Ang(1-7) data have been recorded for all three study days.	
 • Disease diagnosis status
At Risk	
For the purpose of evaluating ACP/PCD and ARDS incidence rates the participants who satisfy
 
1) PASP and RV size ratio recorded for all three study days (regardless of the Ang II and Ang(1-7) status)
 
and/or
 
2) databased ACP/PCD and/or ARDS assessment during the study period (even if they do not have three days' worth of study assessments for the above echo outcomes)
 
provided consent is not withdrawn.
	
 • Disease diagnosis status

NOTES :

1. Please refer to Section 10.10: List of Data Displays which details the population to be used for each display being generated.
2. Modifications to the Completed population listed in study protocol to assist with production of summary and incidence rate calculations for ACP/PCD status (include creating a new population "At Risk" to be used with selected incidence rate displays that is independent of the RAS biomarker availability). The remaining completed population is not formally used, but will provide feasibility information (i.e. could we measure items reliably in the "real world" of the ICU)

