10. APPENDICES

10.1. Appendix 1: Protocol Deviation Management and Definitions for Evaluable Population

10.1.1. Exclusions from Evaluable Population

Subjects with major/important protocol deviations will be considered for exclusion from Evaluable Population. The Protocol Deviation Management Plan (PDMP) will be used to determine major/important protocol deviations that will lead to exclusion from the Evaluable Population (Note: In the event the PDMP retains the template text / default terminology which refers to “per protocol population” it would be interpreted as the “Evaluable population” for study 205821).

In addition, a subject meeting any of the following criteria will be excluded from the Evaluable population (or if more applicable, only the relevant timepoint(s) excluded):

Number	Exclusion Description
01	
Participants whose day 1, day 2 and day 3 samples were all lost or for whom the post sample processing was unable to produce evaluable results would be excluded from the evaluable population
 
If a single day (or two days) are impacted by the above reason(s) then the participant shall remain in the evaluable population, but the impacted time points would be removed from the analysis.

02	
If a single day (or two days) are impacted by the ECHO results that are later deemed of insufficient quality (e.g. this may be discovered by independent review/adjudication of source notes) then those data points would be removed from the analysis (but the participant would remain in the evaluable population). If all of the day 1, day 2 and day 3 ECHO results are impacted in this way then the participant would be removed from the evaluable population.

03	
If the participant takes a prohibited concomitant medication that, in the opinion of the GSK medical monitor, may confound / interfere with the estimation of the true relationship between RAS peptides and an endpoint then any post con-med observations would be removed from the corresponding analysis.

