10.10.4. Study Population Tables

Study Population Tables					
No.	Population	IDSL / Example Shell	Title	Programming Notes	Deliverable [Priority]
Subject Disposition					
1.1.	Enrolled	ES1	Summary of Subject Disposition for the Subject Conclusion Record	ICH E3, FDAAA, EudraCT, CONSORT	SAC 1
1.2.	Screened	ES6	Summary of Screening Status and Reasons for Screen Failure	Journal Requirements	SAC 1
1.3.	Safety	NS1	Summary of Number of Subjects by Country and Site ID	EudraCT/Clinical Operations	SAC 1
Protocol Deviations					
1.4.	Safety	DV1	Summary of Important Protocol Deviations	ICH E3	SAC 1
Population Analysed					
1.5.	Enrolled	SP1A	Summary of Study Populations	IDSL	SAC 1
1.6.	Enrolled	SP2A	Summary of Exclusions from the Safety/Evaluable/Completed/At Risk Populations	IDSL If possible separate page for each population (this may require non-standard wrapper macro to call the standard macro separately for each population) If the Evaluable with prohibited conmed population is different to evaluable add it in (otherwise footnote the evaluable table to indicate they are the same)	SAC 1

Study Population Tables					
No.	Population	IDSL / Example Shell	Title	Programming Notes	Deliverable [Priority]
Demographic and Baseline Characteristics					

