5.4.	Evaluable	SM_T4 (MODEL1)	Summary of Primary Model Results: Ang II as a Predictor of PASP and RV Size Ratio	
On separate pages:
 
Table 1) subtitle: Model Parameters Values with Statistics
 
Table 2) subtitle: PASP and RV Model Predictions for Reference Ang II Values: Pre-dose <Ang_II_level> (pg/mL) and Post-dose <Ang_II_level> (pg/mL)
 
Table 3) subtitle: Probability of RV Dysfunction Given Reference Ang II Values: Pre-dose <Ang_II_level> (pg/mL) and Post-dose <Ang_II_level> (pg/mL)
 
Add any sensitivity reference value results onto separate pages. For clear separation the subtitles start with 'SENSITIVITY.'
	SAC 1

Statistical Modelling: Tables					
No.	Population	IDSL / Example Shell	Title	Programming Notes	Deliverable [Priority]
5.5.	Evaluable	SM_T4 (MODEL2)	Summary of Secondary Model Results: Ang(1-7) as a Predictor of PASP and RV Size Ratio	
On separate pages:
 
Table 1) subtitle: Model Parameters Values with Statistics
 
Table 2) subtitle: PASP and RV Model Predictions for Reference Ang(1-7) Values: Pre-dose < Ang(1-7)_level> (pg/mL) and Post-dose < Ang(1-7)_level> (pg/mL)
 
Table 3) subtitle: Probability of RV Dysfunction Given Reference Ang(1-7) Values: Pre-dose < Ang(1-7)_level> (pg/mL) and Post-dose < Ang(1-7)_level> (pg/mL)
 
Add any sensitivity reference value results onto separate pages. For clear separation the subtitles start with 'SENSITIVITY'.
	SAC 1

Statistical Modelling: Tables					
No.	Population	IDSL / Example Shell	Title	Programming Notes	Deliverable [Priority]
5.6.	Evaluable	SM_T4 (MODEL3)	Summary of Secondary Model Results: Ang(1-5) as a Predictor of PASP and RV Size Ratio	
[conditional output] On separate pages:
 
Table 1) subtitle: Model Parameters Values with Statistics
 
Table 2) subtitle: PASP and RV Model Predictions for Reference Ang(1-5) Values: Pre-dose < Ang(1-5)_level> (pg/mL) and Post-dose < Ang(1-5)_level> (pg/mL)
 
Table 3) subtitle: Probability of RV Dysfunction Given Reference Ang(1-5) Values: Pre-dose < Ang(1-5)_level> (pg/mL) and Post-dose < Ang(1-5)_level> (pg/mL)
 
Only analysis would be the sensitivity reference value, but still start the subtitles with 'SENSITIVITY:'
	SAC 1
5.7.	Evaluable	SM_T4 (MODEL4)	Summary of Secondary Model Results: Ang II and Ang(1-7) as Joint Predictors of PASP and RV Size Ratio	[conditional output] Model only run if data permit	SAC 1

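### The prohibited-medication sensitivity set adds back whole participants, so time points removed from participants who stay Evaluable are not restored

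*SAP*

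**What the plan says.** Three parts of the SAP bear on this.

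- **Removal.** SAP 10.1.1 introduces its criteria as excluding the participant, "or if more applicable, only the relevant timepoint(s) excluded". Item 03 covers a prohibited medication that the sponsor's medical monitor thinks may confound the relationship under study: "then any post con-med observations would be removed from the corresponding analysis". SAP 7.1.4 likewise says that data after a non-permitted medication may have to be left out of the primary analysis.
- **Membership.** SAP 4 counts as Evaluable a participant with PASP, RV size ratio, Ang II and Ang(1-7) at one or more time points "who still had at least one study time point of data remaining after accounting for any prohibited concomitant medications".
- **Sensitivity set.** SAP 4 also defines Evaluable with Prohibited Con Meds as the Evaluable participants "plus any participants who were excluded from the Evaluable population because of prohibited concomitant medications". Its stated use is "Sensitivity for Primary analysis (conditional on number of prohibited con meds"), with no number given as the trigger.

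On display, the programming note to Table 1.6 (SAP 10.10.4) adds this population to the exclusions table if it differs from Evaluable, and "otherwise footnote the evaluable table to indicate they are the same". A note in SAP 4 says that Section 10.10 gives the population for each display. There, the primary model table (Table 5.4, "Summary of Primary Model Results: Ang II as a Predictor of PASP and RV Size Ratio") and every other modelling table, figure and listing name the Evaluable population.

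**The concern.** Data are taken out by time point and put back by participant. Someone with a usable Day 1 who then starts a prohibited drug loses later days but never leaves the Evaluable population. A set made by adding excluded participants has nobody to add in that case, and no text says that the lost days return.

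The removals depend on judgement. Item 03 turns on the medical monitor's opinion, and SAP 4 gives its drug classes only as examples. Protocol 7.1 asks for medications to be recorded and names none as prohibited during the study; the named restriction is exclusion criterion 9 in Protocol 6.2, on RAS modulators before entry. A sensitivity analysis should show whether these judgements drive the Ang II association. As defined, it leaves out the removals made from participants who stay Evaluable.

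**Working it through.** No stated figure needs reproducing; the check applies the SAP's definitions to each possible case.

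**Inputs.** Three assessment days (Protocol, Schedule of Activities). A day is complete if all four measures are usable. Item 03 removes complete days after the drug starts. A participant is Evaluable if at least one complete day is left. The sensitivity set adds a participant only if none is left because of the drug.

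**All three days complete.** The last three columns show how many removed time points return under three readings of what happens to item 03 in the sensitivity set, since the SAP does not say.

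| Drug starts | Removed | Kept | Evaluable? | Item 03 stays in force | Lifted for re-added participants only | Lifted for everyone |
|---|---|---|---|---|---|---|
| Before Day 1 | 3 | 0 | No, so re-added | 0 of 3 | 3 of 3 | 3 of 3 |
| Between Days 1 and 2 | 2 | 1 | Yes | 0 of 2 | 0 of 2 | 2 of 2 |
| Between Days 2 and 3 | 1 | 2 | Yes | 0 of 1 | 0 of 1 | 1 of 1 |

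The definition speaks only of adding participants, so it supports at most the first two readings. Under either, the participants in the last two rows get nothing back. The third reading would work, but no text states it.

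**Some days incomplete.** Count the patterns of complete days in which item 03 removes something, and those in which no pre-drug day is complete, so that the participant is excluded and re-added.

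- Start before Day 1: any non-empty set of days, 2³ − 1 = 7 patterns; no pre-drug day exists, so re-added in 7 of 7.
- Start between Days 1 and 2: Day 2 or 3 or both complete (3 ways) × Day 1 complete or not (2 ways) = 6 patterns; re-added when Day 1 is not complete, 3 of 6.
- Start between Days 2 and 3: Day 3 complete × Days 1 and 2 in any state (2² = 4 ways) = 4 patterns; re-added when neither is complete, 1 of 4.

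These count patterns and are not probabilities; the documents do not say how often each would occur.

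**Displays.** If item 03 removed time points but no whole participant, the two populations have identical members and the Table 1.6 footnote applies. Table 5.4 does provide SENSITIVITY pages, but for the alternative reference values of SAP 7.1.5. The fallback in SAP 7.1.5.1 concerns model form. None of these addresses prohibited medication.

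**The case against.** The strongest reply is that the SAP is silent, not contradictory. It never says that item 03 stays in force in the sensitivity set. The set's name and purpose fit lifting the rule for everyone, and since SAP 10.1.1 lets an exclusion act on single time points, exclusion from the Evaluable population could be read to cover them. This may be what was meant. But SAP 4 speaks of adding participants, and a programmer following it would build a participant flag.

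The same silence defeats one stronger inference: that the sensitivity run applies opposite rules to the same exposure. That requires item 03 to be lifted for re-added participants and kept for the rest, which no passage says.

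Other points stand and limit the concern:

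- A participant-level set does suit one documented route. Protocol 6.2 admits participants whose medication history cannot be obtained, so pre-entry exposure can make every time point a post-drug one.
- The Table 1.6 footnote is true of participant sets. A reader might take it to mean that no data were removed, but it does not say so. Concomitant medications are also summarised and listed (Table 1.11, Listing 7).
- Protocol deviations are reviewed before the final analysis (SAP 3.2 and 4.1), the study was stopped early, and SAP 2.4 tests no formal hypothesis.

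These lower the stakes. They do not put the removed time points into any planned analysis.

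**Conclusion.** The mismatch is real and worth correcting. For a participant with at least one usable time point before the drug, the definition as written restores none of the time points removed under item 03: 0 of 2 for a start between Days 1 and 2 and 0 of 1 for a start between Days 2 and 3, with complete data. For a participant with no such time point, the set restores membership, but it restores data only if item 03 is lifted, which is not stated.

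A reader might infer that removals for any drug started during the study are never tested. The documents do not support that: where no earlier day is usable, the participant is excluded and re-added, and SAP 7.1.4 expects unsuitable echo views and lost samples. Nor can one say that many observations are affected or that the primary result would move. The documents do not give the number of prohibited-drug starts during the study or of observations removed, so the effect on the estimate is unknown.

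The conclusion rests on reading SAP 4 literally, by participant.

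**What to change.** - In SAP 4, define the sensitivity set by observation: every time point with evaluable PASP, RV size ratio, Ang II and Ang(1-7), with item 03 of SAP 10.1.1 not applied to any participant.
- In SAP 10.10.8, assign this set a SENSITIVITY page of Table 5.4, to be produced when item 03 removed observations. This also supplies the trigger that SAP 4 leaves open.
- In Table 1.6, report how many participants and how many observations were removed under item 03, in place of the footnote.

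The cost is SAP wording, an observation-level flag and one extra run of an existing model. No new data are needed.

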4.1. Protocol Deviations

Important protocol deviations (including deviations related to study inclusion/exclusion criteria, conduct of the trial, patient management or patient assessment) will be summarised and listed.

Protocol deviations will be tracked by the study team throughout the conduct of the study in accordance with the current version of the Protocol Deviation Management Plan.

1. Data will be reviewed prior to freezing the database to ensure all important deviations are captured and categorised on the protocol deviations dataset.
2. This dataset will be the basis for the summaries and listings of protocol deviations.

A separate summary and listing of all inclusion/exclusion criteria deviations will also be provided. This summary will be based on data as recorded on the inclusion/exclusion page of the eCRF.

5. CONSIDERATIONS FOR DATA ANALYSES AND DATA HANDLING CONVENTIONS

5.1. Study Treatment & Sub-group Display Descriptors

No study treatment is being administered in this study. However, GSK's standard SAS macro reporting tools will still assign each participant a set of treatment variables ("No treatment"). There will not be any treatment comparisons. Tables and Figures will only be presented with a single "No Treatment" column unless they are presented by covariate groupings or subgroups as described in Section 5.3 below.

5.2. Baseline Definitions

At present, no analyses involving a change from baseline are planned since there is no treatment intervention. However, for each endpoint the Baseline will be defined as the earliest evaluable timepoint (if a baseline is required).

5.3. Examination of Covariates, Other Strata and Subgroups

5.3.1. Covariates and Other Strata

The set of potential covariates and other strata that may be used in descriptive summaries and statistical analyses, some of which may also be used for subgroup analyses are large.

To facilitate flexible model building and analyses a A&R dataset(s) of potential covariate and grouping variables should be constructed (called ARDATA.ALLCVTS). It would be expected to contain three records per participant (Study Day 1, Day 2 and Day 3 values for time-varying covariates), with subject-level covariates repeated across the three records (a flagging variable should also be created to subset the main dataset to extract one record per subject if analyses only involve subject-level covariates); an illustrative example is shown below

Subject	Visit	SUBJLEV	AGE	SEX	SAPSII	ARDSX	ARDSI	...
PPD	Day 1	1	35	M	12	N	N	...
	Day 2	0	35	M	12	N	N	...
	Day 3	0	35	M	12	N	N	...
	Day 1	1	43	F	16	Y	N	...
	Day 2	0	43	F	16	Y	Y	...
	Day 3	0	43	F	16	Y	Y	...
	Day 1...	1	54...	M...	7...	N...	N...	...

Guidance for its construction/algorithms are given in Section 10.6.10.

5.3.2. Examination of Subgroups

The following list of subgroups may be used in descriptive summaries and statistical analyses. Additional subgroups of clinical interest may also be considered based on items in ARDATA.ALLCVTS.

- If the percentage of subjects is small within a particular subgroup, then the subgroup categories may be refined prior to producing the final version of the planned output.
- If the category cannot be refined further, then descriptive rather than statistical comparisons may be performed for the particular subgroup.

Subgroup [ARDATA.ALLCVTS Variable]	Categories
ARDS Status [ARDSX]	ARDS, No ARDS (diagnosed at any time in the study)
Any PCD or ACP [PCDACPX & PCDACPI]	Yes; No (where Yes = Participant had disease state of PCD or ACP) Group can be applied across all study visits [PCDACPX] or to specific days [PCDACPI]
No PCD or ACP [NORVDYSX & NORVDYSI]	Yes; No (where Yes = Participant did not have a disease state of PCD or ACP) Group can be applied across all study visits [NORVDYSX] or to specific days [NORVDYSI]
PCD [PCDX & PCDI]	Yes; No (where Yes implies the worst diagnosis received was Moderate PCD across all study visits [PCDX variable] and Yes implies the worst diagnosis received on the corresponding study day was Moderate PCD [PCDI variable])
ACP [ACPX & ACPI]	Yes; No (where Yes implies the worst diagnosis received was Non-severe ACP across all study visits [ACPX variable] and Yes implies the worst diagnosis received on the corresponding study day was Non-severe ACP [ACPI variable])
Severe ACP [SEVACPX & SEVACPI]	Yes; No (where Yes implies the worst diagnosis received was Severe ACP across all study visits [SEVACPX variable] and Yes implies the worst diagnosis received on the corresponding study day was Severe ACP [SEVACPI variable])
ARDS and No PCD or ACP [ARDNOX]	Yes; No (where Yes implies participant received an ARDS diagnosis but never had PCD or ACP at any time in the study)
ARDS and PCD [ARDPCDX]	Yes; No (where Yes implies participant received an ARDS diagnosis but the worst case diagnosis was Moderate PCD at any time in the study)
ARDS and ACP [ARDACPX]	Yes; No (where Yes implies participant received an ARDS diagnosis but the worst case diagnosis was Non-severe ACP at any time in the study)
ARDS and Severe ACP [ARDSACPX]	Yes; No (where Yes implies participant received an ARDS diagnosis and the worst case diagnosis was Severe ACP at any time in the study)

